11.3 Objection by minors or incapacitated subjects

Not applicable.

11.4 Benefits and risks assessment, group relatedness

This study does not involve any incapacitated or minority groups and is considered a low-risk study. Although volunteers will not benefit directly from participating in this study, the risks associated with participation are minor and proportional to the scientific value of the research. This study can contribute to understanding the putative mechanism of action for taVNS, providing new insights and perspectives for further research into the application of taVNS in pathophysiological states, and potentially leading to new treatment options for various indications.

Subjects will be informed about the risks and burdens associated with the measurements beforehand. However, the burdens and risks of the current study are considered to be minimal to the benefits. The study protocol involves two visits, with the test day having a maximum expected duration of 3 hours. These visits take some time for participants but are not expected to interfere with their regular daily activities.

TaVNS stimulation is a non-invasive treatment approach, and to date, no serious adverse events have been reported in literature. For a detailed overview of previously reported risks of taVNS, see paragraph 6.4 'Summary of known and potential risks and benefits.

Insertion of a nasogastric tube will be performed manually by a doctor, the coordinating investigator, which is considered a safe, routine medical procedure with a low risk of complications. The entire procedure will take only a few minutes and is not expected to cause significant negative effects beyond mild discomfort in the nose or throat, which typically subsides after a short time. While potential complications include aspiration, bleeding, or soreness in the nose or throat, the risk in this study is anticipated to be much smaller, as the procedure will be conducted in young, healthy volunteers without gastrointestinal disorders or other clinical indications, as opposed to patients requiring a nasogastric tube for medical reasons (54). The infusion of a 50% fat emulsion in water is expected to induce nausea. Participants may also experience bloating, abdominal discomfort, cramps, or diarrhea, as fat emulsions can alter gastric emptying and motility. Vomiting may occur with larger fat volumes. Participants will be carefully monitored to manage and reduce any excessive discomfort.

The collection of blood samples can bring along some slight risk, i.e. hematoma, bleeding, pain and/or vasovagal reaction during or after vena puncture. Participants will be seated on an examination bed, to prevent side effects to occur.

Further study procedures involve measurements of salivary cortisol levels and autonomic functions, using the Shimmer3 GSR sensor and Fitbit smartwatch, which carry no risks.

In the event of incidental findings during the study period, the general practitioner will be contacted. If a subject does not wish to be informed of incidental findings, they will not be allowed to participate in the study.

11.5 Compensation for injury

The sponsor/investigator has a liability insurance which is in accordance with article 7 of the WMO. The sponsor (also) has an insurance which is in accordance with the legal requirements in the Netherlands (Article 7 WMO). This insurance provides cover for damage to research subjects through injury or death caused by the study.

The insurance applies to the damage that becomes apparent during the study or within 4 years after the end of the study.

11.6 Incentives

Subjects who complete the entire study, including the screening and test day, will receive a compensation of 150 euros. Furthermore, travel expenses will be compensated, reimbursing €0.23 per kilometre if travelled by car or full reimbursement for public transportation costs. Participants who choose to withdraw before the test day will be compensated for travel expenses but will not receive any additional compensation. In case the participant does not have a nausea response to the lipid infusion and the test day is terminated for this reason, a compensation of 150 euros will be provided.

12. ADMINISTRATIVE ASPECTS, MONITORING AND PUBLICATION

12.1 Handling and storage of data and documents

All obtained data will be handled confidentially and coded to protect the privacy of the participants, in accordance with EU General Data Protection Regulation (Algemene Verordening Gegevensbescherming, 2016) and the Dutch Act on Implementation of the General Data Protection Regulation (Uitvoeringswet Algemene Verordening Gegevensbescherming, 2020).

At study entrance, all subjects are assigned an individual study ID that is not directly traceable to their identity. The code starts with “VNSN” (standing for ‘Vagus Nerve Stimulation Nausea’) to indicate the study, followed by a three-digit participant number in chronological order, starting with “001” for the first subject, and so on (for example: “VNSN001”). The coordinating investigator will keep the key to the code in a locked cabinet, to which only the coordinating and principal investigator have access. In case of inspection, the Inspectie van Gezondheidszorg en Jeugd (IGJ) and the appointed monitor will have access as well.

A Data Management Plan (DMP) will be created in collaboration with an expert from MEMIC. All (coded) data will be stored and analysed at Maastricht University, using a certified database.

The data collection framework will consist of the following elements:

1. Castor EDC for Case report forms (CRF) and questionnaires

Castor EDC is a web-based tool for collecting (clinical) data. Within the electronic CRF, various information will be recorded, including the inclusion and exclusion criteria, the findings of the researcher during the visits, and any adverse events. CRFs will be coded and will not contain personal details of the subjects. Completed validated questionnaires (i.e. baseline characteristics questionnaire, GAD-7, PHQ-9, BFI, and VAS scores) will be saved within Castor EDC. Castor Electronic Data Capture, Ciwit BV, <http://castoredc.com>, Amsterdam, uses “True”, a NEN7510 and ISO 27001:2005 certified server, in line with previous studies performed by our group (PERSUADE and TENDER, NL56000.068.16/METC 162009 and NL62932.068.17/METC 173051 resp.).

2. Shimmer3 GSR sensor

For the Consenys software, an anonymized test subject ID will be used to ensure no traceable data is recorded. The key to this code will be stored securely in a locket

cabinet, accessible only to a select part of the research team, specifically the principal investigator ([name]. [name]) and the coordinating investigator ([name]). All data storage is managed by end users, with Shimmer having no visibility or access to the data. Shimmer adheres to all EU guidelines and directives, ensuring data handling complies with European data protection legislation, including the General Data Protection Regulation (GDPR).

3. FitBit wearable

For the FitBit application, an anonymized test subject ID will be used to ensure no traceable data is recorded. The key to this code will be stored securely in a lockbox cabinet, accessible only to a select part of the research team, specifically the principal investigator ([name]. [name]) and the coordinating investigator (Drs. [name]). All data on phones, on the server and in-transit are encrypted and pseudo-anonymized using industry-standard encryption techniques. Encrypted data from Fitbit will be stored via servers of Amazon Web Services (United States). As a result, data exchange of the encrypted data will take place outside the European Economic Area. However, all parties concerned state that the data exchange is in accordance with European data protection legislation, including the General Data Protection Regulation (GDPR). In addition, we will inform the subjects about the data exchange outside the European Economic Area and the fact that the level of protection for data transfer to countries outside the European Economic Area is not exactly the same as the level of protection for data transfer to countries inside the European Economic Area. We will ask for explicit consent for the data exchange to a country not part of the European Economic Area in the Informed Consent form. Our group previously used the Fitbit applications for similar purposes (DISCOVERIE, NL75159.068.20/METC 20-076 & RESILIENCE, METC23-032 / NL84720.068.23 & tVNS and autonomic responses, METC24-029 / NL87188.068.24).

4. Datahub

All data will eventually be stored in Datahub in accordance with the FAIR principles, the EU General Data Protection Regulation (in Dutch: AVG) and the Dutch Act on Implementation of the General Data Protection Regulation (in Dutch: UAVG). Datahub is a MUMC+ initiative designed to support researchers from MUMC+ and Maastricht University in the field of research data management for both clinical and non-clinical studies. Datahub provides a central infrastructure including an institutional repository for storing metadata and research data. Datasets will be archived in Datahub Maastricht. The datahub infrastructure will ensure that only individuals with the appropriate authorisation can upload new data and access existing data.

All primary documents and data will be stored for 15 years after the end of the study at Maastricht University and will be accessible to the principal investigators ([name]. [name]), coordinating investigator ([name]), the Dutch Health Care Inspectorate (Inspectie Gezondheidszorg en Jeugd), and monitors assigned by the Clinical Trial Center Maastricht (CTCM). Samples taken from the subjects during the study will also be kept for 15 years after the end of the study for possible additional analysis for this study. The label of each sample will contain the individual study ID and the date of collection. The primary investigator ([name]. [name]) and the coordinating investigator ([name]) have access to the stored samples. In the informed consent form, subjects indicate whether they give consent for storing and keeping personal data and biological samples, which may be used for additional analysis in the line of the current investigation. If subjects deny this consent, personal data and biological samples will only be used for the analysis as described in this protocol. By any means, personal data and biological samples will be securely stored for 15 years within Maastricht University.

12.2 Monitoring and Quality Assurance

A qualified monitor of the CTCM will monitor the conduct of the study. A monitoring plan will be drafted after the first application to the METC.

12.3 Amendments

Amendments are changes made to the research after a favourable opinion by the accredited METC has been given. All amendments will be notified to the METC that gave a favourable opinion.

12.4 Annual progress report

The sponsor/investigator will submit a summary of the progress of the trial to the accredited METC once a year. Information will be provided on the date of inclusion of the first subject, numbers of subjects included and numbers of subjects that have completed the trial, serious adverse events/ serious adverse reactions, other problems, and amendments.

12.5 Temporary halt and (prematurely) end of study report

The investigator/sponsor will notify the accredited METC of the end of the study within a period of 8 weeks. The end of the study is defined as the last patient's last visit.

The sponsor will notify the METC immediately of a temporary halt of the study, including the reason of such an action.

In case the study is ended prematurely, the sponsor will notify the accredited METC within 15 days, including the reasons for the premature termination.

Within one year after the end of the study, the investigator/sponsor will submit a final study report with the results of the study, including any publications/abstracts of the study, to the accredited METC.

12.6 Public disclosure and publication policy

Publication will occur in accordance with the CCMO-statement on publication policy (CCMO-statement publicatiebeleid, 2002).

13. STRUCTURED RISK ANALYSIS

13.1 Potential issues of concern

The tVNS R is a transcutaneous vagus nerve stimulation device that will be investigated outside the intended use of declaration of conformity (D2_Declaration_of_conformity_tVNS_L_signed_Versie1.0_31-05-2021).

a. Level of knowledge about mechanism of action

The therapeutic potential of taVNS is hypothesized to result from its ability to influence sensory feedback from the body to the brain. The auricular vagus nerve serves as the target of taVNS, providing a unique access point to the ANS since the external ear is the only location where the vagus nerve sends its only peripheral branch. Modulation of this solely vagal afferent leads to activation of the nucleus of the solitary tract (NTS), which serves as the primary relay station for sensory vagal afferents in the brainstem. The NTS has direct or indirect projections to the nuclei that provide noradrenergic, endorphinergic, and serotonergic fibers to various brain regions (13). Efferent outflow is then generated either via the efferent vagus through the vago–vagal reflex loop or via splanchnic nerves to various organs. Brain imaging studies have shown that taVNS can activate the NTS (55). However, the physiological impact of this activation on vagal or autonomic function in humans remains uncertain and is merely based on assumptions derived from animal studies or invasive VNS (13). Hypotheses suggests that taVNS stimulation may restore reduced vagal tone, which is commonly seen in various diseases, and subsequently restore homeostasis. Nevertheless, there is no conclusive evidence explaining why taVNS elicits therapeutic effects (35).

b. Previous exposure of human beings with the test product(s) and/or products with a similar biological mechanism

Studies have demonstrated the clinical efficacy of VNS in patients with depression (48), migraine (43), epilepsy (39-41), and tinnitus (42), among others. For a more detailed description of these studies, see paragraph 6.3. In addition, a previous study in adolescents with functional abdominal pain has also shown promising results of vagal neuromodulation (16).

c. Can the primary or secondary mechanism be induced in animals and/or in ex-vivo human cell material?

TaVNS has been investigated in mice (34) and rats (33). See paragraph 6.2 for further details regarding these studies.

d. Selectivity of the mechanism to target tissue in animals and/or human beings

Not applicable.

e. Analysis of potential effect

The tVNS device is considered safe. Previous studies have shown no serious or long-lasting adverse events (40, 45-47). See paragraph 6.4 'summary of known potential risks and benefits' for previously reported risks.

f. Pharmacokinetic considerations

Not applicable.

g. Study population

All participants are healthy volunteers aged 18-65 years. No risks have been identified for this population (see also paragraph 6.2). Vagus nerve stimulation has been applied to both healthy controls and patient populations for several years (56-59).

h. Interaction with other products

Not applicable.

i. Predictability of effect

Not applicable.

j. Can effects be managed?

In healthy humans, taVNS has been demonstrated to be a safe and well-tolerated procedure, particularly in individuals without a history of cardiac disease (37, 45, 46). Subjects with cardiac pathology or pacemakers will be excluded from the study. However, autonomic parameters will be monitored continuously throughout the taVNS stimulation and nausea induction period. No serious complications have been reported in literature. A few subjects have reported dizziness, fatigue, concentration problems and a tingling sensation at the ear, which are typically associated with longer stimulation durations or with higher stimulation intensities (47). Therefore, prior to the experiment, the stimulation current will be adjusted according to each subject's sensitivity to ensure it remains below the pain threshold. Participants are allowed to withdraw from the study at any time.

13.1.2 Potential concerns related to the co-intervention

The introduction of a nasogastric tube poses no significant risks, although it may cause temporary discomfort in the nose or throat. The infusion of a 50% fat emulsion in water is expected to induce nausea. Participants may also experience bloating, abdominal discomfort, cramps, or diarrhea, as fat emulsions can influence gastric emptying and

motility. With higher fat volumes, vomiting may occur. Participants will be closely monitored to manage and minimize excessive discomfort. Rescue medication will be used in case nausea symptoms are too severe.

13.2 Synthesis

TaVNS is a non-invasive and a safe approach to use in research. The risks associated with participation in this study are minor and proportional to the scientific value of the research. Serious adverse events have not been reported in studies examining the efficacy of the tVNS device. Mild to moderate adverse events, including dizziness, fatigue, concentration problems, and a tingling sensation at the ear, have been reported. However, these symptoms typically and quickly disappear after removing the tVNS device. It is anticipated that this study will reveal important insights into the physiological impact of taVNS on vagal and autonomic function in healthy individuals, with an expected reduction in nausea severity.

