5.3 Escape medication

To ensure participant safety, an ondansetron dissolvable tablet will be administered as escape medication when nausea reaches a severity level of 80 or higher out of 100 on the VAS scale, indicating severe discomfort and an imminent vomiting sensation. Following the immediate termination of the lipid infusion, a single dose of 4 mg will be given, with a maximum of four doses (16mg total) allowed per day if necessary. Based on previous research using more intensive nausea induction methods, including intraduodenal lipid infusion and gastric distension, in which 2 out of 12 healthy participants experienced vomiting, we do not expect frequent vomiting in our study (10).

Ondansetron is a well-established anti-emetic that exerts its effects primarily through antagonism of 5HT₃ (serotonin) receptors. It is commonly used for the management of nausea in clinical settings (32). See D6.4_Ondansetron_SPC_Versie1.0_dd 22-07-2024 for additional information.

Given that participants will be healthy volunteers, it is anticipated that no contraindications, such as relevant medication use, will be present. However, if ondansetron is administered, participants will be closely monitored for both relief from nausea and potential side effects, including headache, dizziness, and other known reactions, for at least 1 hour following administration.

The decision to administer ondansetron will be documented, including the time of administration, the participant's reported nausea level, and any subsequent symptoms.

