6.4 Summary of known and potential risks and benefits

Transcutaneous vagus nerve stimulation is a non-invasive treatment that is generally well-tolerated and safe in patients without pre-existing cardiac pathology (45, 46). Thus far, no serious risks have been mentioned in the literature. Some studies have reported occasional side effects, such as dizziness or daytime drowsiness during prolonged stimulation, which alleviated upon reducing the stimulation intensity (40). In a pilot study, taVNS exhibited no serious or long-lasting side effects, and no significant heart rate changes were observed during stimulation. Some participants experienced temporary fatigue, concentration difficulties, or a tingling sensation at the stimulation site, which subsided within 90-minutes (47). In a randomized controlled trial involving adolescents, using a more invasive method percutaneous electrical nerve field stimulation, eight individuals discontinued treatment due to aesthetic reasons, discomfort from the device's fit, needle phobia, or anxiety, as well as adhesive allergy (16). However, these concerns are less relevant in the current study, as it employs ear electrodes that fit comfortably without the need for plasters and stimulate the vagus nerve in a non-invasive, transcutaneous manner. In addition, patients may experience slight hearing impairment on the side where the electrode is placed. A recent systematic review and meta-analysis reported no serious adverse effects with taVNS. Mild symptoms of dizziness, headache, and slight redness around the stimulation area were noted, all of which resolved shortly

after discontinuing the intervention (48). Furthermore, taVNS can be provided safely both left and right-sided, as was illustrated by a review article (49).

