8.2 Randomisation, blinding and treatment allocation

After confirming suitability for inclusion and obtaining written informed consent during the initial visit, participants will be scheduled for a second visit (referred to as the test day). Prior to this test day, an investigator will randomise the subjects in a 1:1 parallel fashion to receive either taVNS or sham stimulation. The randomisation of participants will be conducted using Castor, an electronic data capture system. The concealment list will be generated and provided to a co-worker in the same department as the coordinating investigator. For emergencies, drs. [name] will be provided with the concealment list and will be able to de-blind. The concealment list provides information on which participant will get active taVNS and who will get

sham stimulation. This information will remain confidential, and the concealment list will be sealed until after the initial analysis.

In this study, blinding procedures will be implemented. The tVNS device used will be identical for both the active and sham groups, and the ear electrodes will be placed at the same anatomical location. Furthermore, the device will blink in both groups to ensure that participants remain blinded to their treatment allocation. The key differences are that the sham group will receive a device with a non-conducting electrode, and that the electrodes for the taVNS and sham groups will be slightly different. As a result, the investigator responsible for programming the devices on the test day will be aware of treatment allocation. To maintain proper blinding for the initial analysis, the randomization code will be changed prior to the data analysis using Castor. The randomization code will be kept confidential until after the modified intention-to-treat analysis has been reported.

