9.2 AEs, SAEs and SUSARs

9.2.1 Adverse events (AEs)

Adverse events are defined as any undesirable experience occurring to a subject during the study, whether or not considered related to transcutaneous auricular vagal nerve stimulation or the nausea induction by intragastric lipid infusion. All adverse events reported spontaneously by the subject or observed by the investigator, or his staff will be recorded. Subjects are promptly asked to report any changes in their health in the 24 hours following the test day via phone or email to the coordinating investigator. These adverse events will then be recorded in Castor.

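### The known, mostly subjective effects of taVNS are not asked about uniformly in all participants, so mild device effects are likely to be under-recorded and the counts are open to ascertainment bias

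*Protocol*

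**What the plan says.** **Known effects.** Section 13.2 states "Mild to moderate adverse events, including dizziness, fatigue, concentration problems, and a tingling sensation at the ear, have been reported", and 13.1(j) gives a similar list. Section 6.4 adds drowsiness, headache, local redness and slight hearing impairment on the stimulated side. For one pilot study, 6.4 reports temporary fatigue, concentration difficulties or "a tingling sensation at the stimulation site, which subsided within 90-minutes". Section 13.2 expects symptoms to go quickly once the device is removed.

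**Capture rule for everyone.** Section 9.2.1: "All adverse events reported spontaneously by the subject or observed by the investigator, or his staff will be recorded". It also asks every participant to tell the coordinating investigator, by phone or email, of health changes over the 24 hours after the test day, with entry in Castor. Section 9.4 has recorded events followed until they abate or stabilise.

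**Test-day questionnaires (8.3.4).** Nausea, abdominal pain, bloating and fullness are scored at 14 time points and desire to eat at four. None of the device effects above is included.

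**After ondansetron (5.3).** Rescue is given "when nausea reaches a severity level of 80 or higher out of 100 on the VAS scale". Participants who receive it are then "closely monitored for both relief from nausea and potential side effects, including headache, dizziness, and other known reactions" for at least an hour, and subsequent symptoms are documented.

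**Who knows the arm.** Section 8.2: "the investigator responsible for programming the devices on the test day will be aware of treatment allocation". Section 8.3.2 has the coordinating investigator prepare the device and adjust the current.

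**The concern.** Dizziness, fatigue, poor concentration, headache and tingling reach the record only if the participant thinks to mention them. Participants are there to report nausea and are asked about it every five minutes. A brief tingle or light-headedness may well go unmentioned.

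The device is used outside the intended use in its declaration of conformity (sections 6 and 13.1), and 13.1(j) ties these effects to stimulation duration and intensity. Readers will therefore want to know how well this trial's settings were tolerated. An analysis plan cannot recover symptoms that nobody asked about, so this belongs in the protocol.

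A second issue is who receives the reports. If the person who notes an event knows the arm, attention and recording may differ by arm, even though the written rule is the same for both.

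**Working it through.** **1. Matching each known effect to a capture route**

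| Effect (6.4, 13.1, 13.2) | Visible to staff? | On a test-day questionnaire? | Named for monitoring? |
|---|---|---|---|
| Dizziness | Hardly | No | Only after ondansetron |
| Headache | Hardly | No | Only after ondansetron |
| Fatigue/drowsiness | Partly | No | No |
| Concentration problems | Hardly | No | No |
| Tingling at the ear | No | No | No |
| Slight hearing impairment | Hardly | No | No |
| Redness | Yes | No | No |

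The visibility column is a judgement. The other two columns follow from 8.3.4 and 5.3.

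**2. Timing.** The 24-hour request covers the period after the test day. Section 6.4 reports resolution within 90 minutes and 13.2 expects it soon after device removal. The request therefore looks mainly at a time when these effects should be gone. The last nausea VAS comes 30 minutes after stimulation ends, inside the 90-minute window.

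**3. Who receives the reports.** Section 8.2 says that the programming investigator knows the arm. Section 8.3.2 gives device preparation to the coordinating investigator, and 9.2.1 sends the 24-hour reports to the same role. That these are one person is a reasonable inference, but the protocol does not state it.

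**4. Arm size.** Section 4.4 uses a difference of 25 mm, SD 21.5, two-sided alpha 0.05 and power 0.80. An unpaired t-test gives 12.65, rounded up to 13 per arm, or 26 in total (power 0.812). This reproduces the stated 26. Thirteen per arm assumes that the 1:1 ratio holds among responders.

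**5. Effect of under-capture.** The documents give neither a true event rate *p* nor a captured share *s*; both are assumed. The chance of recording no case in 13 is (1 − *p*·*s*)^13.

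| Assumed *p* | *s* = 1 | *s* = 0.5 | *s* = 0.25 |
|---|---|---|---|
| 10% | 0.90^13 = 0.25 | 0.95^13 = 0.51 | 0.975^13 = 0.72 |
| 20% | 0.80^13 = 0.05 | 0.90^13 = 0.25 | 0.95^13 = 0.51 |
| 30% | 0.70^13 = 0.01 | 0.85^13 = 0.12 | 0.925^13 = 0.36 |

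Even with full capture, 0 of 13 leaves a one-sided 95% upper bound of 1 − 0.05^(1/13) = 20.6%.

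**6. When would the arms differ?** With equal true rates, the observed risk difference is *p* × (*s* in one arm − *s* in the other).
- Equal capture gives a difference of 0 at any *p*.
- Capture of 0.75 against 0.50, purely as an illustration, gives 0.10 × 0.25 = 2.5 points up to 0.30 × 0.25 = 7.5 points. That is 13 × 0.025 = 0.3 to 13 × 0.075 = 1.0 event per arm.

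A spurious difference therefore needs capture to differ by arm, through the recorder's knowledge of allocation or through unequal ondansetron use. The documents give no figure for either.

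**The case against.** The strongest objection is that one defined rule applies to both arms and participants are stated to be blinded. Every participant is asked to report health changes for 24 hours, is seen every five minutes for an hour, and is assessed before leaving on well-being and symptom resolution (8.3.2). Recorded events are followed to resolution (9.4). Tolerability is neither an objective nor an endpoint, and section 10 plans no between-arm test of adverse events. Such a test would be nearly powerless: at 13 per arm, a true 30% against 15% gives about 7% power (Fisher's exact test, two-sided 0.05). The case report form is not shown and might contain prompts.

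Most of this is correct and limits the point. It does not remove it. The five-minute contacts ask about nausea and other gastrointestinal symptoms. The check before leaving centres on nausea and independent function. Follow-up helps only for an event already recorded. Section 9.2.1 itself states the capture rule, and it contains no prompting for these effects.

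A reader might go further and infer that, because headache and dizziness are looked for after ondansetron, and sham participants would need more of it if taVNS works, the two arms' adverse event counts are not comparable and favour taVNS. The documents do not support that. The rescue trigger is a nausea score and is the same in both arms. Section 5.3 links ondansetron to termination of the infusion, which comes before stimulation. Rescue may also be uncommon, because the infusion stops at a score of 50. Later rescue is not excluded, but no rescue rate is given, and nothing shows that monitoring after ondansetron captures every event. With equal rescue use in both arms, this route produces no bias.

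**Conclusion.** The point holds in limited form. The protocol names a set of mostly subjective device effects but does not ask all participants about them, and the person who receives the reports appears to know the arm. Under-recording of mild effects is likely. Ascertainment bias between arms is possible but not shown.

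The size rests on assumed rates. At true rates of 10–30% with half of cases captured, the chance of recording no case in 13 active participants is 51% down to 12%, against 25% down to 1% with full capture. The sample size and the primary analysis are unaffected. Section 13.2 is not itself in error: it lists effects from previous studies, and its expectation of quick resolution does not conflict with the 90 minutes in 6.4. The text to change is in 9.2.1 and 8.3.2. This is a worthwhile, inexpensive improvement and does not threaten the trial's main conclusion.

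**What to change.** In 9.2.1 and 8.3.2, add one fixed checklist in Castor. Every participant in both arms, whether or not given ondansetron, completes it personally after the last nausea VAS and the final samples. It covers the effects already named in 6.4 and 13.2: dizziness, drowsiness or fatigue, concentration problems, headache, tingling, redness, and hearing on the stimulated side. Each item has two yes/no answers: present during stimulation, and still present now.

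Summarise the checklist descriptively by arm. List spontaneous reports, and events found only through monitoring after ondansetron, separately.

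Self-completion keeps the answers from passing through an investigator who knows the arm. The late timing means that the questions cannot influence the nausea scores or the samples.

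The cost is 1–2 minutes per participant and a protocol amendment, with no added staff, procedures or participants. Mild-event counts will be higher in both arms than under spontaneous reporting, and with about 13 per arm the table remains descriptive.
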